#### Treatment-related Adverse Event (TRAE)

A treatment-related AE is any treatment-emergent AE that per investigator review has a reasonable possibility of being caused by the investigational product (either AMG 330 or pembrolizumab or in combination of AMG 330 and pembrolizumab).

## Dose Limiting toxicity (DLT)

Investigators will determine whether an adverse event qualifies as a DLT per protocol Section 6.2.1.

### Duration of Response (DOR)

Duration of response is calculated for subjects who have achieved overall response (CRMRD-, CR, CRi, PR or MLFS). It is defined as time from the first observation indicating an objective response to the subsequent date of disease progression or death, whichever is earlier.

Protocol Number: 20170646

**Date:** 25 August 2020 Page 17 of 35

DOR time in days: (date of disease progression or death - date of the first observation of objective response +1)

DOR time in months: (date of disease progression or death - date of the first observation of objective response +1)/30.4

Subjects without disease progression or death until the analysis data cut-off date will be censored at the last adequate disease assessment date.

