Dexamethasone (8 mg IV) should be administered within 1 hour prior to re-start and within 1 hour prior to each AMG 330 dose step(s). Dexamethasone is not required prior to the pembrolizumab administration unless it co-occurs with the AMG 330 step dose. In cases when administration of pembrolizumab co-occurs with AMG 330 step, pembrolizumab is administered first followed by dexamethasone followed by AMG 330. The subject should be hospitalized starting from re-start of infusion until 72 hours after the dose step. After each dose level increase, vital signs will be obtained as per the Schedule of Activities (see [Table 1-1](#), [Table 1-3](#), [Table 1-5](#)).

The number of days of exposure to both investigational products before and after an interruption should sum up to at least 70% of planned cumulative dose of AMG 330. In this case, the subject would still be DLT-evaluable. However, if the cycle was interrupted for more than 24 hours but less than 21 days, a new repeat cycle should be started and the interrupted cycle would not be evaluable for DLT, unless the event that lead to the interruption was a DLT.

Note: The end of infusion bone marrow assessment should be performed once it is confirmed that the cycle will not be resumed to assess treatment response. [REDACTED]

[REDACTED]

[REDACTED].

Permanent Discontinuation

A subject will permanently discontinue treatment with investigational product in the event of:

- Dose-limiting or other unmanageable toxicity. Exception: If a DLT occurs in a subject with a clear clinical benefit from treatment a restart at a lower dose can be considered if the toxicity has resolved and after consultation with the sponsor. This includes:
 - Grade 4 CRS
 - Grade 3 CRS occurring at the initial step dose for a cycle (ie, at the 10 µg/day)
 - Grade 2 or 3 CRS meeting any of the criteria listed below:
 - Grade 2 or 3 CRS that does not improve to ≤ grade 1 within 7 days
 - Grade 3 CRS that does not improve to ≤ grade 2 within 5 days
- Re-occurrence of the same grade 4 adverse event
- 3 infusion interruptions > 24 hours in cycle 1
- Disease progression as defined by 2017 European LeukemiaNet (ELN) criteria ([Döhner et al, 2017](#))
- Withdrawal of subject's consent to treatment
- Subject or investigator not compliant with the study protocol
- Occurrence or progression of a medical condition which in the opinion of the investigator should preclude further participation of the subject in the study

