- Hematological or extramedullary relapse subsequent to CR/CRh*/CRI/MLFS on protocol treatment. Exception: a blast count > 5% at the pre-dose assessment (after the infusion-free interval) would not lead to permanent treatment discontinuation even if the count had been < 5% directly after the previous treatment cycle.
- An infusion interruption of more than 21 days due to an adverse event not clearly related to the underlying disease.

- Occurrence of CNS-related adverse event considered related to AMG 330 by the investigator and meeting 1 or more of the following criteria:
 - More than 1 seizure
 - A CNS-related adverse event CTCAE grade 4
 - A CNS-related adverse event leading to treatment interruption that needed more than 1 week to resolve to CTCAE grade ≤ 1
- Non-manageable GVHD
- Investigator's decision that a change of therapy is in the subject's best interest
- Administration of relevant non-permitted concomitant medications

Women who become pregnant while on study through 1 week after receiving the last dose of study drug will not receive subsequent scheduled doses and will be followed for safety until the end of study visit.

Men with pregnant partners or whose partners become pregnant while the subject is on study will receive subsequent scheduled doses and must practice sexual abstinence or use a condom while on study through 120 days after receiving the last dose of study drug.

All reasons for treatment discontinuation should be clearly and concisely documented in the eCRF. If a subject has not continued to present for study visits, the investigator should determine the reason and circumstances as completely and accurately as possible.

In any case of premature treatment discontinuation, the investigator should make every effort to perform all examinations scheduled for the end of treatment and safety follow-up visits. These data should be recorded, as they comprise an essential evaluation that should be performed prior to discharging any subject from the study and to allow for the evaluation of the study endpoints.

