**Date:** 25 August 2020 Page **34 of 35** 

Appendix D. European LeukemiaNet (ELN) Response Criteria in Acute Myeloid Leukemia (2017)

Category	Definition	Comment				
Response	Response					
CR without minimal residual disease (CR MRD -)	If studied pretreatment, CR with negativity for a genetic marker by RT–qPCR, or CR with negativity by MFC	Sensitivities vary by marker tested, and by method used; therefore, test used and sensitivity of the assay should be reported; analyses should be done in experienced laboratories (centralized diagnostics)				
Complete remission (CR)	Bone marrow blasts < 5%; absence of circulating blasts and blasts with Auer rods; absence of extramedullary disease; ANC ≥ 1.0 x 10  /L (1000/µL); platelet count ≥ 100 x 10  /L (100 000/µL)	MRD + or unknown				
CR with incomplete hematologic recovery (CRi)	All CR criteria except for residual neutropenia (< 1.0 x 10  /L [1000/μL]) or thrombocytopenia (< 100 x 10  /L [100 000/μL])					
Morphologic leukemia-free state (MLFS)	Bone marrow blasts < 5%; absence of blasts with Auer rods; absence of extramedullary disease; no hematologic recovery required	Marrow should not merely be "aplastic"; at least 200 cells should be enumerated or cellularity should be at least 10%				
Partial remission (PR)	All hematologic criteria of CR; decrease of bone marrow blast percentage to 5 to 25%; and decrease of pretreatment bone marrow blast percentage by at least 50%	Especially important in the context of phase 1/2 clinical trials				
Treatment failure	Treatment failure					
Primary refractory disease	No CR or CRi after 2 courses of intensive induction treatment; excluding patients with death in aplasia or death due to indeterminate cause	Regimens containing higher doses of cytarabine are generally considered as the best option for patients not responding to a first cycle of 7+3; the likelihood of responding to such regimens is lower after failure of a first				
Death in aplasia	Deaths occurring ≥ 7 days following completion of initial treatment while cytopenic; with an aplastic or hypoplastic bone marrow obtained within 7 days of death, without evidence of persistent leukemia					
Death from indeterminate cause	Deaths occurring before completion of therapy, or < 7 days following its completion; or deaths occurring ≥ 7 days following completion of initial therapy with no blasts in the blood, but no bone marrow examination available					

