**Protocol Number: 20170646** 

**Date:** 25 August 2020 Page 35 of 35

Category	Definition	Comment
Response criteria for clinical trials only		
Stable disease	Absence of CR MRD- , CR, CRi, PR, MLFS; and criteria for PD not met	Period of stable disease should last at least 3 months
Progressive disease (PD)*	Evidence for an increase in bone marrow blast percentage and/or increase of absolute blast counts in the blood:  • 50% increase in marrow blasts over baseline (a minimum 15% point increase is required in cases with < 30% blasts at baseline; or persistent marrow blast percentage of > 70% over at least 3 months; without at least a 100% improvement in ANC to an absolute level (> 0.5 x 10  /L [500/μL], and/or platelet count to > 50 x 10  /L [50 000/μL] nontransfused); or  • 50% increase in peripheral blasts (WBC x % blasts) to > 25 x 10  /L (> 25 000/μL) (in the absence of differentiation syndrome) ¶ ; or  • New extramedullary disease	Category mainly applies for older patient given low-intensity or single-agent "targeted therapies" in clinical trials In general, at least 2 cycles of a novel agent should be administered Some protocols may require blast increase in 2 consecutive marrow assessments at least 4 weeks apart; the date of progression should then be defined as of the first observation date  Some protocols may allow transient addition of hydroxyurea to lower blast counts "Progressive disease" is usually accompanied by a decline in ANC and platelets and increased transfusion requirement and decline in performance status or increase in symptoms
Relapse		
Hematologic relapse (after CR MRD –, CR, CRi)	Bone marrow blasts ≥ 5%; or reappearance of blasts in the blood; or development of extramedullary disease	
Molecular relapse (after CR MRD -)	If studied pretreatment, reoccurrence of MRD as assessed by RT–qPCR or by MFC	Test applied, sensitivity of the assay, and cutoff values used must be reported; analyses should be done in experienced laboratories (centralized diagnostics)

Page 2 of 2

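### Duration of response ends only at progression or death, so a relapse after CR or CRi that falls short of ELN progression is censored or dated late

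*SAP*

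**What the plan says.** SAP Section 5.4 calculates DOR for subjects who reach CR without MRD, CR, CRi, PR or MLFS. It runs from "the first observation indicating an objective response to the subsequent date of disease progression or death, whichever is earlier", and both formulas, in days and in months, use only the progression or death date. The censoring rule follows: "Subjects without disease progression or death until the analysis data cut-off date will be censored at the last adequate disease assessment date". The Protocol names DOR as a secondary endpoint but does not define it.

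SAP Appendix D reproduces the ELN 2017 criteria, with progressive disease and relapse as separate entries. Haematologic relapse, after CR without MRD, CR or CRi, is "Bone marrow blasts ≥ 5%; or reappearance of blasts in the blood; or development of extramedullary disease". Progression by marrow is a 50% "increase in marrow blasts over baseline (a minimum 15% point increase is required in cases with < 30% blasts at baseline" (Protocol Section 11.11 prints it as more than 50%). The other routes to progression are marrow blasts persistently above 70% for at least 3 months, a more than 50% rise in peripheral blasts to above 25 x 10^9/L, and new extramedullary disease.

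Protocol Section 6.2.2.1 also lists the two separately as reasons for permanent discontinuation: "Disease progression as defined by 2017 European LeukemiaNet (ELN) criteria" and "Hematological or extramedullary relapse subsequent to CR/CRh*/CRI/MLFS on protocol treatment". It adds an exception to the second: "a blast count > 5% at the pre-dose assessment (after the infusion-free interval) would not lead to permanent treatment discontinuation".

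SAP Section 9.5.2 commits to presenting DOR per subject. Kaplan-Meier estimates are optional.

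**The concern.** ELN progression by marrow is judged against the pretreatment baseline, whereas relapse is judged against remission. A subject in CR whose marrow returns to 5% blasts or more, but stays below the progression level, has lost the response without producing a DOR event. Two things can then happen:

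- The subject is censored, possibly at the very assessment that showed the relapse. That censoring is informative.
- Progression or death is recorded later, and the response is credited with the interval in between.

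Both push Kaplan-Meier DOR upward. In the per-subject presentation, a relapsed subject appears without an end event. The listed duration is too long only where later assessments, progression or death follow the relapse.

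The study hypothesis is that the combination deepens and prolongs remission, and DOR is the endpoint that addresses how long remission lasts.

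**Working it through.** **No DOR figure to reproduce.** The documents give no assumed median or event count for DOR. The one context figure used here does reproduce: Protocol Section 4.3 reports 5 responders of 39 on AMG 330 monotherapy, 5/39 = 12.8%, with an exact 80% interval of 6.4% to 22.5%, as stated.

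**Gap between relapse and progression.** Inclusion criterion 104 admits any baseline above 5% marrow blasts. For baseline *b* (%), progression by marrow rise requires blasts above max(1.5*b*, *b* + 15) if *b* < 30, and above 1.5*b* otherwise. Relapse requires 5%.

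| Baseline | Progression by marrow rise | Relapse |
|---|---|---|
| 10% | > 25% | ≥ 5% |
| 20% | > 35% | ≥ 5% |
| 40% | > 60% | ≥ 5% |
| 60% | > 90% | ≥ 5% |
| 67% | > 100.5%, unattainable | ≥ 5% |

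From a baseline of about 67% only the blood, extramedullary and persistent > 70% routes remain. In blood the gap is similar: any reappearance of blasts is relapse, but progression needs more than 25 x 10^9/L. New extramedullary disease satisfies both definitions, so that form of relapse is not affected.

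**Will a later event be recorded?** Relapse normally ends treatment (Protocol Section 6.2.2.1). Safety visits follow 30 (+7) days after the last dose of each drug (8.1.3), and long-term follow-up is not applicable (8.1.4). Vital status is required for all subjects (8.2.4.3), so some deaths will be captured, but as late DOR events. Assume the time from relapse to progression or death is exponential with median *m* months, and that data capture continues *w* months after relapse. The share of these relapsers left censored is exp(−ln 2 × *w*/*m*):

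- *w* = 1: 0.71, 0.79 and 0.84 for *m* = 2, 3 and 4.
- *w* = 6: 0.125, 0.25 and 0.35 for *m* = 2, 3 and 4.

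**Small illustration (assumed data).** Four CR/CRi responders relapse at 2, 3, 4 and 6 months, none meeting progression at relapse.

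- Relapse as an event: S = 0.75, 0.50, 0.25, 0, so 50% is reached at 3 months.
- As written, progression or death 3 months later in all four (5, 6, 7, 9): 50% is reached at 6 months.
- As written, 3 months later in two of the four, the other two censored at relapse: over the six possible pairs, S ≤ 0.5 is first reached at 5, 6, 6, 7, 7 or 7 months.
- As written, neither recorded in any: S stays at 1 and the median is not reached.

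**Simulation (all inputs assumed).** 400,000 exponential responders per scenario; median time to relapse 3, 4 or 6 months; median time to death without relapse 30 months; cut-off 24 months; 25% to 75% of relapses also meeting progression when detected. Kaplan-Meier median DOR in months:

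| Median time to relapse | Relapse counted | Other relapses censored | Other relapses counted late (median lag 2 months) |
|---|---|---|---|
| 3 | 2.7 | 3.5–8.6 | 3.3–4.6 |
| 4 | 3.5 | 4.5–10.4 | 4.1–5.5 |
| 6 | 5.0 | 6.3–13.3 | 5.6–6.9 |

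The shift is upward in every scenario.

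**Scale.** At 12.8%, 20 subjects give 20 × 0.128 = 2.56 responders. The binomial probability of at least 2 is 0.75 and of at least 4 is 0.25.

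**The case against.** The strongest reply is that SAP Section 5.4 does not cite the ELN progressive-disease entry, so a programmer could read progression broadly enough to include relapse. In support, the removal reasons in Protocol Section 7.1 include disease progression but not relapse. The opening of Section 6.2.2.1 also continues AMG 330 until progression, although relapse stops it too. This reading does not hold. Section 7.1 also has an entry for protocol-specified criteria, which covers a relapse stop. Section 6.2.2.1 ties progression to ELN, and no text folds relapse into it.

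A second reply concerns scale. One of the five earlier responders had MLFS, and Appendix D defines relapse only after CR without MRD, CR or CRi. Counting only CR and CRi gives 4/39 = 10.3%, or about 2.1 of 20 subjects, and a probability of about 0.14 of four or more. However, Section 6.2.2.1 recognises relapse after MLFS, so those responders can also lose response before ELN progression. On either count the numbers are very small.

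A third reply is that the exception for a pre-dose count above 5% shows the protocol does not treat every such rise as the end of benefit. That exception governs treatment and not DOR. It does show that the SAP must say how DOR handles the case.

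What stands is that DOR is descriptive, no hypothesis is tested, Kaplan-Meier is optional and may not be worth fitting with two or three responders, and only the direction of the bias comes from the documents.

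**Conclusion.** The concern holds. As written, a subject in CR without MRD, CR or CRi whose marrow or blood blasts return below the ELN progression level has no DOR event, and is either censored or counted late. The bias in Kaplan-Meier DOR is upward whenever at least one such relapse occurs. Its size cannot be read from the documents. In the four-subject illustration the time to 50% moves from 3 months to between 5 and 7 months, or is not reached, depending on assumed follow-up. The consequence is limited because no decision rule uses DOR, but with about 2.6 expected responders one misclassified relapse can determine what is reported on durability. It should be fixed.

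**What to change.** Before database lock, amend SAP Section 5.4, both DOR formulas and the censoring sentence as follows:

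- After CR without MRD, CR or CRi: DOR runs from first response to the earliest of haematologic or extramedullary relapse (Appendix D), ELN progressive disease, or death. Censor at the last adequate assessment only if none of these occurred.
- After PR: do not apply the 5% marrow criterion, since PR itself is a "decrease of bone marrow blast percentage to 5 to 25"%. Use ELN progression or death, or state an explicit blast rise.
- After MLFS: progression, death or loss of its own criteria (marrow blasts of 5% or more, blasts with Auer rods, or extramedullary disease). Circulating blasts alone should not end it, because MLFS does not require their absence.
- State whether molecular relapse after CR without MRD counts.
- State how DOR treats a pre-dose blast count above 5% after the infusion-free interval.

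The cost is SAP wording plus some programming. SAP Section 5.5 names only a Disease Response CRF page, so relapse dates may have to be derived from marrow and blood results. The one drawback is a shorter reported DOR.

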### 5.5 Treatment Response

Treatment response is defined in Appendix D. The data will be recorded on Disease Response CRF page.

## 6. Analysis Sets

The analysis of all endpoints, unless noted otherwise, will be conducted on the Safety Analysis Set defined in Section 6.1

### 6.1 Safety Analysis Set

Safety Analysis Set defined as all subjects that are enrolled and receive at least 1 dose of AMG 330 or pembrolizumab.

# 6.2 Dose Limiting Toxicity (DLT) Evaluable Analysis Set

Dose limiting toxicity evaluable Analysis Set is defined as DLT-evaluable subjects in the Safety Analysis Set (see definition of DLT-evaluable in Section 6.2.1. of the protocol). The analysis of DLT will be conducted on the DLT evaluable Analysis Set.

## 6.3 Pharmacokinetic Analyses Set(s)

The PK Analysis Set will contain all subjects who have received at least 1 dose of the AMG 330 or pembrolizumab and have at least 1 PK sample collected.

### 7. Planned Analyses

# 7.1 Interim Analysis and Early Stopping Guidelines

Safety data will be reviewed on an ongoing basis. The dose level review meeting (DLRM) will occur when at least 10 treated subjects in cohort 1 have been dosed through study day 28 to determine if the safety profile of initial steps in cohort 1 is acceptable to begin enrollment of cohort 2 or if the study should be stopped. If 3 or more of the 10 treated subjects in cohort 1 experience a DLT by day 28, the guidance to the DLRT is to recommend not to initiate cohort 2. The stopping rule is based on having at least a posterior probability of > 70% that the DLT rate is > 20% assuming a prior distribution of Beta (0.40, 1.60). If the true DLT rate is 10%, 20%, 30%, 40%, or 50%,

Protocol Number: 20170646

Date: 25 August 2020 Page 18 of 35

then the probability of stopping the study at the interim analysis is 7%, 32%, 62%, 83%, 95%, respectively.

# 7.2 Primary Analysis

The primary analysis will occur when all subjects have ended study.

## 7.3 Final Analysis

The primary analysis will also be the final analysis.

### 8. Data Screening and Acceptance

### 8.1 General Principles

The objective of the data screening is to assess the quantity, quality, and statistical characteristics of the data relative to the requirements of the planned analyses.

## 8.2 Data Handling and Electronic Transfer of Data

The Amgen Global Study Operations-Data Management (GSO-DM) department will provide all data to be used in the planned analyses. This study will use the RAVE database.

### 8.3 Handling of Missing and Incomplete Data

The following imputation for missing or incomplete data will be performed if required:

Incomplete adverse event and concomitant medication dates missing data will be imputed as described in Appendix A.

### 8.4 Detection of Bias

Lack of protocol compliance and the potential for biased statistical analyses will be examined by assessing the incidence of important protocol deviations. The clinical study team will identify and document the criteria for important protocol deviations following Amgen SOP.

### 8.5 Outliers

Outlier data will not be excluded unless scientifically justified.

PK concentration data will be evaluated for outliers by visual inspection and decisions to re-assay individual samples will be made in accordance with standard CPMS practices. All excluded observations will be detailed by CPMS along with reasons for exclusion, in accordance with standard CPMS practices.

Protocol Number: 20170646

**Date:** 25 August 2020 Page 19 of 35

## 8.6 Distributional Characteristics

Where appropriate, the assumptions underlying the proposed statistical methodologies will be assessed. If required data transformations or alternative non-parametric methods of analyses will be utilized.

## 8.7 Validation of Statistical Analyses

Programs will be developed and maintained, and output will be verified in accordance with current risk-based quality control procedures.

Tables, figures, and listings will be produced with validated standard macro programs where standard macros can produce the specified outputs.

The production environment for statistical analyses consists of Amgen-supported versions of statistical analysis software; for example, the SAS System version 9.4 or later.

## 9. Statistical Methods of Analysis

## 9.1 General Considerations

Descriptive statistics will be provided for selected demographics, safety, PK, and data overall and by cohort and time as appropriate. Descriptive statistics on continuous data will include means, medians, standard deviations and ranges, while categorical data will be summarized using frequency counts and percentages. Graphical summaries of the data may also be

Confidence intervals (CI) for proportions will be estimated using an exact method proposed by Clopper and Pearson (1934).

